2. STATISTICAL HYPOTHESES

The primary hypothesis of this study is that among participants who have treatment-resistant MDD with a current moderate to severe depressive episode, the proportion of participants achieving remission at the Week 8 visit is greater in participants treated with flexibly dosed esketamine nasal spray than in participants treated with quetiapine XR, both administered in combination with a continuing SSRI/SNRI.

The key secondary hypothesis of this study is that among participants who have treatment-resistant MDD with a current moderate to severe depressive episode, the proportion of participants who achieved remission at the Week 8 visit and remain relapse-free through the Week 32 visit is greater in participants treated with esketamine nasal spray than in participants treated with quetiapine XR, both administered in combination with a continuing SSRI/SNRI.

3. SAMPLE SIZE DETERMINATION

For the primary endpoint, the assumptions are that the rate of remission for completers at the Week 8 visit is 50% in the esketamine arm and 35% in the comparator arm, and that the rate for participants who discontinue study intervention between baseline and the Week 8 visit is 17.5% in both treatment arms (to be imputed as non-remitters). Combining these assumptions leads to an estimated remission rate at the Week 8 visit in non-responder imputation (NRI) analysis of 41.25% in the esketamine arm and 28.88% in the comparator arm. With a power of 90%, a 2-sided significance level of 0.05 and using chi-square test, a sample size of 311 participants per arm (622 participants in total) is needed to detect the difference between the study intervention arms.

For the key secondary endpoint, among participants who achieve remission at the Week 8 visit, a relapse rate of 30% is assumed for both study intervention arms and rates for participants who discontinue study intervention between the Week 8 and Week 32 visits (to be imputed as non-relapse-free after remission) is assumed to be 10% for the esketamine arm and 20% for the comparator arm. Combining these assumptions leads to an estimated rate of relapse-free after remission at the Week 32 visit in NRI analysis of 25.99% in the esketamine arm and 16.17% in the comparator arm. With a power of 80%, a 2-sided significance level of 0.05 and using a chi-square test, a sample size of 270 randomized participants per arm (540 participants in total) is needed to detect a difference between the study intervention arms.

4. POPULATIONS (ANALYSIS SETS) FOR ANALYSIS

The following analysis sets will be used in this SAP:

Analysis Sets	Description	
Enrolled Analysis Set	All participants who sign the ICF	
Full Analysis Set (FAS)	The full analysis set includes all randomized	
	participants.	

Analysis Sets	Description	
Safety Analysis Set	The safety analysis set includes all randomized participants who received at least 1 dose of any study	
	intervention.	
Follow-up Analysis Set	The follow-up analysis set includes all randomized	
	participants who received at least 1 dose of any study	
	intervention, and who discontinue study intervention.	

5. STATISTICAL ANALYSES

5.1. General Considerations

5.1.1. Visit Windows

As participants do not always adhere to the protocol visit schedule, the following rules are applied to assign actual visits (or data collection dates) to analysis visits. The reference day is Study Day 1 (Baseline). If a participant has 2 or more actual visits in 1 visit window, the visit closest to the target day will be used as the analysis visit for that visit window. The other additional visit(s) will not be used in the summaries or analyses, but they can be used for determination of clinically important endpoints. If 2 actual visits are equidistant from the target day within a visit window, the later visit is used.

All assignments will be made in chronological order. Once a visit date is assigned to a visit window, it will no longer be used for a later time point except for the endpoint. In Excel sheet "*Visit_windows_v3.xlsx*" are the analysis visit windows and the target days for each visit associated to the different parameters defined in the protocol.

The above procedure will be used for all visits except for the Week 8 visit and the Week 32 visit. For both Week 8 and Week 32 visit, the actual visit with the nominal visit label will be assigned to the corresponding analysis visit.

5.2. Participant Dispositions

Screened participants and reason for screen failures will be summarized overall.

The number of participants in the following disposition categories will be summarized throughout the study by intervention group and overall:

- Participants randomized
- Participants who received study intervention
- Participants who completed the study

The number of participants in the following disposition categories will be summarized for the first 8 weeks of the study, for the second part (week 9-32) and overall, by intervention group:

- Participants who discontinued study intervention
- Reasons for discontinuation of study intervention
- Participants who terminated study prematurely
- Reasons for termination of study

A listing of participants will be provided for the following category:

• Participants who were randomized yet did not receive study intervention.

5.3. Primary Endpoint Analysis

5.3.1. Definition of Endpoint

The MADRS is a clinician-rated scale designed to measure depression severity and to detect changes due to antidepressant treatment. The MADRS consists of 10 items that cover all of the core depressive symptoms (apparent sadness, reported sadness, inner tension, sleep, appetite, concentration, lassitude, interest level, pessimistic thoughts, and suicidal thoughts). Each item is scored from 0 (item is not present or is normal) to 6 (severe or continuous presence of the symptom). A total score (0 to 60) is calculated by adding the scores of all 10 items. For each item as well as the total score, a higher score represents a more severe condition. If 2 or more items are missing, no imputation will be performed, and the total score will be left missing. Otherwise, the total score will be calculated as the sum of the items present multiplied by the ratio of the maximum possible number of items (i.e., 10) to the number of items present.

The primary endpoint is remission at the Week 8 visit, defined as a MADRS total score of ≤ 10 .

5.3.2. Estimand

Primary Trial Objective: to evaluate the efficacy of flexibly dosed esketamine nasal spray compared with quetiapine XR, both in combination with a continuing SSRI/SNRI, in achieving remission at the Week 8 visit in participants who have treatment resistant MDD with a current moderate to severe depressive episode.

Estimand Scientific Question of Interest: What is the proportion of participants considered to have benefited from esketamine versus quetiapine XR for the pre-specified duration (8 weeks), administered in combination with a continuing SSRI/SNRI?

Study intervention:

- Flexibly dosed esketamine nasal spray in combination with a continuing SSRI/SNRI
- Quetiapine XR in combination with a continuing SSRI/SNRI.

Population: Participants

- 18 to 74 years of age (inclusive) with treatment resistant MDD
- on a current antidepressive treatment that includes an SSRI/SNRI that resulted in nonresponse, but the participant shows signs of minimal clinical improvement
- must have documented nonresponse within the current moderate to severe depressive episode to at least 1 but not more than 5 different, previous consecutive treatments with ADs taken at an adequate dosage for an adequate duration of at least 6 weeks, and that each prior AD treatment did not produce any significant improvement
- must have been treated with at least 2 different antidepressive substance classes among the failed treatments in the current depressive episode.

Variable: Remission (binary variable), where remission is defined as a participant achieving a MADRS total score of ≤ 10 at the Week 8 visit, who does not before week 8 visit:

- discontinues (any component of) study intervention, or
- withdraws from the study.

Summary measure (population-level summary): Difference in proportions.

Intercurrent events and their corresponding strategies:

Intercurrent Events	Strategy for Addressing Intercurrent Events and its Description
Discontinuation of (any component of) study intervention for any reason	Composite Strategy : A participant with this intercurrent event is considered as a non-responder after this event, the occurrence of this intercurrent event being captured in the variable definition
Withdrawal from the study	Composite Strategy: Same as above

In the main analysis, for subjects who do not have an available MADRS result at the Week 8 visit but did not discontinue study intervention or withdraw from study before Week 8, LOCF of MADRS will be applied. In a sensitivity analysis, these subjects will be considered a nonresponder.

5.3.3. Analysis Methods

The efficacy analysis of data will be based on the full analysis set. Statistical analysis test will be conducted at a two-sided 0.050 level of significance.

The rate of remission at the Week 8 visit will be tested between study intervention arms using a Cochran-Mantel-Haenszel (CMH) chi-square test adjusting for age (18 to 64 years [inclusive]; 65 to 74 years [inclusive]) and total number of treatment failures (2; 3 or more). The estimate of the treatment difference in proportions, the odds ratio and their 95% CI will be reported. In the main analysis, the variables age and number of treatment failures will be based on CRF data. A sensitivity analysis will be performed using IXRS data.

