1.3. Schedule of Activities

1.3.1. Schedule of Activities (Weeks 1 to 8)

Phase	Screening	Acute phase													
Week	W-2 to -1			W1		W2		W3		W4	W5	W6	W7	W8	
Day – Esketamine arm	D-14 to 0 ^a	D1 ^a	D4	D8	D11	D15	D18	D22	D25	D29	D36	D43	D50	D57	
Day – Comparator arm	D-14 to 0 ^a	D1 ^a	-	D8	-	D15	-	D22	-	D29	-	D43	-	D57	
Visit Window (Days)			±1	±1	±1	±1	±1	±1	±1	±1	±2	±2	±2	±2	
Administrative Procedures		•			•			•							
Informed consent	Х														
Informed consent - optional biomarker, DNA/RNA		Х													
Inclusion/exclusion criteria	Х	Х													
Document nonresponse to prior AD treatment	Х														
Document nonresponse/minimal clinical improvement to current AD	v	wh													
treatment	х	A°.													
MINI	Х														
IDS-C30	X	Х													
Medical and psychiatric history, demographics, employment status	Х														
Prestudy therapy and elective procedures	Х														
Pregnancy testing ^c	Х	Х								Х				Х	
12-lead ECG (local)	Х	Xď												X	
Physical examination/nasal examination ^e	Х														
Height	Х														
Urine screen for drugs of abuse (local)		Xf													
Document investigator discussion with the participant regarding															
psychotherapy		Xg													
Randomization		Х													
Patient-reported outcomes ^h															
PHQ-9		Х				X				Х		Х		X	
QLDS		Х								Х				X	
EQ-5D-5L		Х								X				Х	
SF-36		Х								Х				X	
SDS		Х								Х				X	
WPAI:D		Х								X				X	
Clinician-rated scales and questionnaires ⁱ															
C-SSRS (Baseline-Screening version)	Х														
C-SSRS (Since Last Visit version)		X		X		X		X		X				X	
MADRS: efficacy assessment/blinded rater		X		X		X				X		X		X	
CGI-S	X	X		X		X		Х		X				X	
CGI-C				X		X		Х		X				X	

									-						
Phase	Screening	g Acute phase													
Week	W-2 to -1			W1		W2		W3		W4	W5	W6	W 7	W8	
Day – Esketamine arm	D-14 to 0 ^a	D1 ^a	D4	D8	D11	D15	D18	D22	D25	D29	D36	D43	D50	D57	
Day – Comparator arm	D-14 to 0 ^a	D1 ^a	-	D8	-	D15	-	D22	-	D29	-	D43	-	D5 7	
Visit Window (Days)			±1	±1	±1	±1	±1	±1	±1	±1	±2	±2	±2	±2	
Study intervention assessments															
Therapeutic benefit assessment (esketamine arm) ⁱ										Х					
Treatment continuation assessment (participants taking study															
intervention) ^{i,j}														X	
Safety assessments															
Hematology/chemistry (central), urinalysis (local) ^k	X	Xl												X	
TSH (FT4 if TSH is out of range)	Х													Х	
Body weight	Х									Х				Х	

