5.1. Inclusion Criteria

Each potential participant must satisfy all of the following criteria to be enrolled in the study:

- 1. male or female, 18 years (or older if the minimum legal age of consent in the country in which the study is taking place is >18 years) to 74 years of age, inclusive, at the time of signing the ICF.
- 2. at screening, each participant must meet DSM-5 diagnostic criteria for single-episode MDD or recurrent MDD, without psychotic features, based on clinical assessment and confirmed by the MINI (see Section 8.1.1.1).
- 3. at screening and baseline, each participant must have an IDS-C30 total score of \geq 34 (see Section 8.1.1.1).
- 4. criterion changed per Amendment 1.
- 4.1 must be on a *current* antidepressive treatment that includes an SSRI/SNRI at screening that resulted in nonresponse (less than 25% improvement of symptoms) after having been given at an adequate dosage (based on antidepressive dosages from SmPC [or local equivalent, if applicable]) for an adequate duration of at least 6 weeks and having been uptitrated to the maximum tolerated dose; however, at screening the participant must show signs of minimal clinical improvement to be eligible for the study. (See also exclusion criterion 4.)

Clinical improvement of a participant on their current AD treatment will be retrospectively evaluated in a qualified psychiatric interview performed by an experienced clinician; additional guidance for this interview is provided in Section 8.1.1.1.

At baseline (Day 1) prior to randomization, the investigator will evaluate any changes in the participant's signs/symptoms of depression since the screening assessment and confirm that the inclusion criteria for the current AD treatment are still met (ie, nonresponse and minimal clinical improvement).

- 5. criterion changed per Amendment 1.
- 5.1 the current antidepressive treatment was immediately preceded by nonresponse to at least 1 but not more than 5 different consecutive treatments (all within the current moderate to severe antidepressive episode) with ADs taken at an adequate dosage for an adequate duration of at least 6 weeks and must be documented (as described in Appendix 3, Regulatory, Ethical, and Study Oversight Considerations: Source Documents) during screening.
- 6. criterion changed per Amendment 1.

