9.4.2. Efficacy Endpoints

The efficacy analyses of data will be based on the full analysis set defined in Section 9.3.

The rate of remission at the Week 8 visit (primary endpoint) and the rate of remission at the Week 8 visit without relapse up to the Week 32 visit (key secondary endpoint) will be tested between study intervention arms using a Cochran-Mantel-Haenszel (CMH) chi-square test adjusting for age (18 to 64 years [inclusive]; 65 to 74 years [inclusive]) and total number of treatment failures (2; 3 or more). Participants will be considered as having a positive outcome on relapse-free after remission if they are in remission at the Week 8 visit and do not experience any relapse between the Week 8 and Week 32 visits. All other cases (participants not achieving remission at the Week 8 visit, or participants achieving remission at the Week 8 visit but experiencing a relapse between the Week 8 and Week 32 visits) will be considered as having a negative outcome. Both the primary and key secondary endpoints will be analyzed using a NRI approach as defined in Section 9.1. In sensitivity analyses, for participants who stopped study intervention, but are still followed in the study, no imputation will be performed, and their observed status will be used for the analyses.

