A total of 622 participants will be randomly assigned on Day 1 (baseline) in a 1:1 ratio to 1 of 2 open-label study intervention arms (311 participants per arm). The randomization will be balanced by using randomly permuted blocks and will be stratified by age (18 to 64 years [inclusive]; 65 to 74 years [inclusive]) and total number of treatment failures (2; 3 or more [inclusive of current antidepressive treatment at screening used to determine eligibility]).

Esketamine arm

Participants will continue to take their current SSRI/SNRI in combination with esketamine nasal spray.

On Day 1, participants will have their first nasal treatment session. Adult participants aged 18 to 64 years will start with a dose of 56 mg. Elderly participants aged 65 to 74 years and adults of Japanese ancestry will start with a dose of 28 mg. As of Day 4, the dose may be increased from 56 mg to 84 mg in adult participants, from 28 mg to 56 mg in elderly participants and adults of

Japanese ancestry, or participants may remain at the starting dose, as determined by the investigator based on efficacy and tolerability. Elderly participants and adults of Japanese ancestry may be uptitrated in 28 mg increments at subsequent visits. The highest dose that may be used in all participants is 84 mg. Nasal treatment sessions will occur twice weekly during Week 1 to Week 4, once weekly during Week 5 to Week 8, and once weekly or every 2 weeks, as determined by the investigator based on efficacy and tolerability, during the maintenance phase (Week 9 to Week 32). Dosing may be increased at any visit, may remain the same, or may be reduced as determined by the investigator based on efficacy and tolerability. Nasal treatment sessions should not take place on 2 consecutive days. Esketamine nasal spray dosing and related safety-monitoring procedures MUST be performed LAST at all visits. Esketamine nasal spray must NOT be administered before all other visit assessments are completed. Food will be restricted for at least 2 hours before each administration of esketamine nasal spray at each session.

Comparator Arm

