5.4.1.3. Analysis Methods

The efficacy analysis of data will be based on the full analysis set. Statistical analysis test will be conducted at a two-sided 0.050 level of significance.

The rate of remission at the Week 8 visit *and* having no relapse within the consecutive 24 weeks until the end of the prospective observation period at Week 32 visit will be tested between study intervention arms using a Cochran-Mantel-Haenszel (CMH) chi-square test adjusting for age (18 to 64 years [inclusive]; 65 to 74 years [inclusive]) and total number of treatment failures (2; 3 or more). The estimate of the treatment difference in proportions, the odds ratio and their 95% CI will be reported. In the main analysis, the variables age and number of treatment failures will be based on CRF data. A sensitivity analysis will be performed using IXRS data.

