5.5. Supportive Secondary Endpoint(s)

5.5.1. General Analysis Methods

For continuous/ordinal parameters (eg, MADRS, CGI-S, PHQ-9, EQ-5D-5L, SF-36, SDS, WPAI:D) descriptive statistics of the score or values and change from baseline will be provided for each study visit during the study for the full analysis set. For CGI-C descriptive statistics of the score will be provided for each study visit during the study by study intervention for the full analysis set. Summaries of both observed and last observation carried forward (LOCF) data will be presented. The change from baseline at each visit will be analyzed using a mixed model for repeated measurements based on observed cases. The model will include baseline score as a covariate, and study intervention, stratification factors (age [18 to 64 years (inclusive); 65 to 74 years (inclusive)] and total number of treatment failures [2; 3 or more]), visit, and visit-by-study intervention interaction as fixed effects applying an unstructured covariance matrix. In case of issue with convergence of the model, alternative structures of variance-covariance matrix will be tested. The change from baseline at each visit will also be analyzed using an analysis of covariance model including LOCF data with factors for treatment, stratifications factors (age [18 to 64 years

(inclusive); 65 to 74 years (inclusive)] and total number of treatment failures [2; 3 or more]) and baseline score as a covariate. For all model approaches, LS estimates of the treatment differences at each visit and 95% confidence intervals will be presented. Additionally, for the MMRM model, the LS mean change from baseline averaged over all visits will be presented with 95% confidence interval per treatment group. The corresponding treatment difference will be presented with 95% confidence interval and two-sided p-value.

Additionally, for scales that have a minimum clinically important difference (MCID), the proportion of participants having improved by at least the MCID will be described at each visit and compared between study interventions using CMH chi-square test adjusting for age (18 to 64 years [inclusive]; 65 to 74 years [inclusive]) and total number of treatment failures (2; 3 or more). The same analysis will be conducted for the proportion of participants who deteriorate by at least the MCID.

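### The two confirmatory CMH tests are valid but leave Day 1 MADRS unused, and the SAP drops the protocol's severity subgroup without declaring it

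*SAP*

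**What the plan says.** **Endpoint.** SAP 5.3.1: "The primary endpoint is remission at the Week 8 visit, defined as a MADRS total score of" 10 or less. The key secondary endpoint is that remission followed by no relapse to Week 32.

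**Tests.** SAP 5.3.3 specifies for the primary a "Cochran-Mantel-Haenszel (CMH) chi-square test adjusting for age" group and number of treatment failures (2; 3 or more). SAP 5.4.1.3 uses the same method and factors for the key secondary: the rate up to the end of the "prospective observation period at Week 32 visit will be tested between study intervention arms using a Cochran-Mantel-Haenszel (CMH) chi-square test". Protocol 9.4.2 agrees: both rates "will be tested between study intervention arms using a Cochran-Mantel-Haenszel (CMH) chi-square test adjusting for age" group and number of failures. The listed sensitivity analyses change the handling of a missing Week 8 MADRS, of participants followed after stopping study intervention, or of the source of the stratification data. None brings in baseline severity.

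**Baseline severity.** Randomisation "will be stratified by age (18 to 64 years [inclusive]; 65 to 74 years [inclusive]) and total number of treatment failures", not by severity (SAP 1.2). In the schedule of activities (Protocol 1.3.1), the row "MADRS: efficacy assessment/blinded rater" is marked on Day 1. Entry severity is set on another scale: "at screening and baseline, each participant must have an IDS-C30 total score of" 34 or more (Protocol 5.1). For the repeated-measures analysis of each continuous scale, SAP 5.5.1 states: "The model will include baseline score as a covariate"; its ANCOVA does the same.

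**Subgroups.** The protocol synopsis and Protocol 9.4.3 commit to subgroup analyses by age group, number of failures, sex and severity of depression; only geographical region is optional. SAP 5.8.7 lists sex, age group, number of failures and class of continued oral antidepressant. SAP Appendix 2 declares one change from the protocol, to the time-to-relapse analysis. The SAP version history does not mention subgroups.

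**The concern.** A fixed cut-off is harder to reach from a higher starting score, so Day 1 MADRS is a natural prognostic covariate for remission. The plan uses it for MADRS change but not for the MADRS-based primary and key secondary endpoints. Two things are lost: some precision, and a pre-specified answer if the arms differ by chance in severity on Day 1. An adjustment chosen after seeing the data would be less credible.

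The subgroup point is a plain mismatch between documents. The trial enrols moderate to severe episodes, so whether the effect is similar across severity is an obvious question, and the protocol promised to look at it. It has disappeared from the SAP for the study report with no reason given. It is exploratory and bears on no confirmatory conclusion.

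**Working it through.** **1. Reproduce the planned sample sizes** (inputs: Protocol 9.2 and SAP 3). Two-sided α = 0.05, pooled-variance chi-square formula, no continuity correction:

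n per arm = [1.960·√(2p̄q̄) + z_power·√(p₁q₁ + p₂q₂)]² / (p₁ − p₂)²

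- Primary: p₁ = 0.50 × 0.825 = 0.4125; p₂ = 0.35 × 0.825 = 0.28875; difference 12.4 points. n = (1.3226 + 0.8575)² / 0.12375² = 310.4, so 311. Power at 311 is 90.1%.
- Key secondary: p₁ = 0.4125 × 0.70 × 0.90 = 0.2599; p₂ = 0.28875 × 0.70 × 0.80 = 0.1617; difference 9.8 points. n = (1.1305 + 0.4819)² / 0.098175² = 269.8, so 270. Power at 311 is 85.3%.

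Both planned figures match.

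**2. Share of outcome variance explained by Day 1 MADRS.** Assumptions not in the documents: Week 8 MADRS in those who continue is latent-normal and correlated r with Day 1 MADRS; discontinuation and relapse are unrelated to Day 1 MADRS. With completer remission rate c, probability s of no later failure, p = cs, and φ(z_c) the normal density at the c-quantile:

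R² = [s·r·φ(z_c)]² / [p(1 − p)], averaged over the arms.

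- Primary (s = 0.825; φ = 0.399 and 0.370): 0.447r² and 0.455r², mean 0.451r².
- Key secondary (s = 0.825 × 0.63 and 0.825 × 0.56): 0.224r² and 0.216r², mean 0.220r².

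The variance of the risk difference is multiplied by (1 − R²). At 311 per arm:

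| r | R² primary | Primary power | n per arm for 90% | R² key secondary | Key secondary power |
|---|---|---|---|---|---|
| 0 | 0 | 90.1% | 311 | 0 | 85.3% |
| 0.2 | 0.018 | 90.6% | 306 | 0.009 | 85.6% |
| 0.3 | 0.041 | 91.2% | 299 | 0.020 | 86.0% |
| 0.4 | 0.072 | 92.1% | 289 | 0.035 | 86.5% |
| 0.5 | 0.113 | 93.1% | 276 | 0.055 | 87.2% |

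The IDS-C30 entry rule truncates severity, which favours the low end of the range.

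**3. Check by simulation.** 10,000 trials per setting, 622 participants, stratified permuted blocks of 4; 15% aged 65 to 74 and 40% with 3 or more failures (both assumed). The four-stratum CMH test is compared with a standardised logistic risk difference.

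| r | Primary, CMH → adjusted | Variance ratio | Key secondary, CMH → adjusted | Variance ratio |
|---|---|---|---|---|
| 0.2 | 89.9 → 90.5% | 1.020 | 85.3 → 85.7% | 1.008 |
| 0.3 | 90.6 → 91.4% | 1.032 | 85.3 → 86.0% | 1.020 |
| 0.4 | 90.6 → 92.8% | 1.077 | 86.0 → 87.2% | 1.028 |
| 0.5 | 90.3 → 93.4% | 1.120 | 85.7 → 87.5% | 1.062 |

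The Monte Carlo standard error of each power figure is about 0.3 points; each pair comes from the same simulated trials. On the primary, the ratios equal 622 × 0.020 ≈ 12 to 622 × 0.120 ≈ 75 extra participants. At r = 0 nothing is lost (90.0% both ways). Null rejection in favour of esketamine was 2.2 to 2.7% (CMH) and 2.3 to 2.5% (adjusted) on the primary, and 2.1 to 2.7% and 2.2 to 2.7% on the key secondary. In a separate run with a linear risk-difference model, CMH two-sided type I error was 5.3%, 5.2% and 4.8% at r = 0, 0.3 and 0.5, and adjustment left the mean risk difference at about 0.124.

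**4. Chance imbalance.** The 95% limit for the arm difference in standardised Day 1 MADRS is 1.96 × √(2/311) = 0.157 SD. Multiplied by the mean slope s·r·φ(z_c):

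- Primary: 0.157 × 0.317r, or 1.0 to 2.5 points for r = 0.2 to 0.5, against a planned 12.4.
- Key secondary: 0.157 × 0.189r, or 0.6 to 1.5 points, against 9.8.

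**5. What a severity subgroup can show.** With a 50:50 split (155.5 per arm), the 95% CI half-width is 1.96 × √[(0.4125 × 0.5875 + 0.28875 × 0.71125)/155.5] = 10.5 points. A 30:70 split gives 13.6 and 8.9. That supports estimation, not testing.

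**The case against.** The CMH test adjusts for exactly the randomisation factors, follows the protocol and holds its type I error. No power shortfall needs repair: the primary meets 90%, and the key secondary has 85.3% against a planned 80%. The gain rests on a correlation absent from the documents, and at the more plausible low end it is about 1 point or less. Chance imbalance is already covered by the test's error rate; the shifts above are 95%-limit cases, not expected bias, and regression removes only what the fitted model captures. MADRS change is already baseline-adjusted and MADRS is summarised by arm at each visit, so an imbalance would be seen. Replacing a protocol-specified confirmatory test in an open-label trial, when SAP version 2 is dated 12 September 2022, needs care. SAP 1 also allows further SAPs for supplementary analyses.

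Much of this stands. It makes the first part an improvement rather than a correction, and it favours a supportive analysis over replacing the CMH test. It does not remove the point: the continuous-scale models do not adjust the binary endpoints, and seeing an imbalance is not the same as having a pre-specified way to handle it. On the subgroup, the possibility of other SAPs does not declare a protocol commitment as dropped; SAP 1 says this SAP covers the planned analyses for the study report.

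**Conclusion.** Both parts hold, and both are modest. The CMH tests and the sample size are sound. Leaving out Day 1 MADRS forgoes up to about 1 point of power on either endpoint for r up to 0.3, and about 3 points (primary) or 2 points (key secondary) at r = 0.5. Counting discontinuers as failures whatever their baseline dilutes the gain. These sizes rest on the assumed r and the latent-normal model; the simulation also rests on assumed stratum proportions. The missing severity subgroup needs no assumption: the protocol commits to it, the SAP omits it, and the change record is silent. Neither part threatens the validity of a confirmatory conclusion. Both should be dealt with because the remedy is cheap.

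**What to change.** 1. For both endpoints, pre-specify a logistic regression with treatment, age group, number of failures and continuous Day 1 MADRS, standardised over the full analysis set to give the difference in proportions with a robust 95% CI. This keeps the SAP's summary measure; a conditional odds ratio would not. State a rule for a missing Day 1 MADRS, and fix the analysis before anyone sees outcome data by arm. A supportive analysis beside the CMH test is enough and costs one SAP paragraph and a few lines of code. Making it the main analysis is possible but debatable, and must be declared in SAP Appendix 2 as a departure from Protocol 9.4.2.
2. Restore severity in SAP 5.8.7, with a cut-point on baseline MADRS or IDS-C30 fixed before database lock, because the protocol names neither scale nor threshold. Report estimates with CIs. Otherwise, record and justify its removal in Appendix 2. The added antidepressant-class subgroup should be listed there too. The cost is one table row and a chosen cut-point, or one sentence.
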